9.4.3 SAFETY ANALYSES

To assess safety of treatment interventions, we will describe adverse events by treatment group and compare by treatment group. We will additionally examine self-reported bothersome symptoms based on response to the HIV Symptom Index, numbers of hospitalizations and ED visits overall and by treatment group.

9.4.4 BASELINE DESCRIPTIVE STATISTICS

Randomization adequacy will be assessed by comparing the differences of baseline demographic and clinical characteristics among intervention groups.

9.4.5 PLANNED INTERIM ANALYSES

No interim looks are planned.

9.4.6 SUB-GROUP ANALYSES

To examine whether treatment differences vary among subgroups, we will conduct exploratory

9.4.7 AND HYPOTHESIS GENERATING ANALYSES. WE WILL STUDY WHETHER TREATMENT EFFECTS DIFFER BY DEMOGRAPHIC AND CLINICAL CHARACTERISTICS COMMON AMONG PWH AND KNOWN TO BE ASSOCIATED WITH TOBACCO USE: DEPRESSION, ALCOHOL USE.TABULATION OF INDIVIDUAL PARTICIPANT DATA

N/A

9.4.8 EXPLORATORY ANALYSES

Exploratory Analysis. We will determine the overall best strategy with regard to 24-week abstinence. There are four strategies to compare: 1) NRT followed by VAR or bupropion in non-responders; 2) NRT followed by NRT+CM in non-responders; 3) NRT+CM followed by VAR or bupropion+CM in non-responders; 4) NRT+CM followed by NRT+CM+ in non-responders. Choosing the optimal strategy is an estimation rather than hypothesis testing problem. Weighted logistic regression will be used to estimate 24-week abstinence rates for each of the strategies. Inverse probability weighting will account for non-

responders being re-randomized and thus split in two groups as they will be underrepresented relative to responders. The analysis will include parameters for the initial randomization group as well as site, age, gender and HSI as baseline covariates. Predicted probabilities and 95% confidence intervals will be estimated for each of the strategies. The strategy with the highest predicted probability will be identified as the optimal strategy.

We will additionally examine "dose response effects" and examine the impact of number of completed interventions sessions as measure of intensity of intervention on outcomes.⁷

We will conduct exploratory analyses by subgroups (see 9.4.6).

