4 STUDY DESIGN

4.1 OVERALL DESIGN

Description of the Study Design

To address aims 1 and 2, we plan to use a two-arm, two-stage randomized trial design of 632 patients with HIV who smoke cigarettes and receive their HIV care in one of three health systems.

To address aim 3, we plan to hold pre- and post-trial surveys involving clinicians, staff, clinical leadership, social workers, psychologists, and care coordinators to conduct an implementation focused-evaluation of a clinical pharmacist-delivered intervention.

Description of Procedures Being Performed

For aims 1 and 2, at baseline, intake history, demographics, questionnaires relating to depression, drug and alcohol problems, smoking habits, medication adherence, HIV symptoms and quality of life will be performed. The depression, substance use, quality of life questionnaires, HIV symptom index and costs related to tobacco use and clinic travel will be administered at weeks 12 and 24. Tobacco measures will be performed at all time points - relating to carbon monoxide levels, cigarette consumption, nicotine dependence, tobacco use and e-cigarette use. HIV related measures pertaining to CD4 count, viral load and other lab values, health care utilization (ED visits, hospitalizations), and treatment services to address tobacco use will be collected at baseline, week 24 and month 12. Patient satisfaction, opinions about services and adherence will also be recorded. At baseline, participants will be randomized 1:1 to either NRT (nicotine replacement therapy) or NRT + CM. Participants will receive a prescription for 12 weeks of the long-acting NRT patches and short-acting NRT (i.e., gum, lozenges, an inhaler or spray) with standard advice. Participants will fill the prescription through their usual pharmacy of choice.

Participants will be invited to complete five follow-up visits with the clinical pharmacist over the following 12 weeks to address medication adherence, side effects and review progress in achieving smoking abstinence. For those randomized to additionally receive contingency management (CM), these visits will be integrated into the sessions with the clinical pharmacist. At week 12, participants who responded to initial treatment will continue without change. Participants who do not respond to the intervention, will be re-randomized, to switch to either VAR or bupropion or intensify to CM+.

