For secondary outcomes of CD4 cell count, HIV viral load and VACS index weighted linear mixed models will be used to estimate mean outcomes at 12 and 24 weeks for each of the treatment strategies. A random effect will be included for repeated measures and the analysis will include indicators for first and second randomization, time, the interactions of first/second randomization indicators with time as well as covariates for baseline outcome, site, age and gender. Inverse probability weighting will be used to account for non-responders being re-randomized. Least squares means and 95% confidence intervals will be estimated. Evaluation of initial treatment strategies at 12 and 24 weeks will be performed using linear mixed models. These analyses will include fixed effects for initial treatment, time and their interaction as well as covariates for baseline outcome, site, age and gender and a random effect for subject to accommodate repeated measures. Similar linear mixed models of only non-responders will be used to evaluate second stage treatment.

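### As written, the four-strategy analyses do not yield valid strategy estimates: no second-stage term for abstinence, no rule for entering responders, no suitable variance, and no workable weighting mechanism

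*Combined protocol and SAP*

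**What the plan says.** Section 9.4.8 (exploratory) compares four strategies on 24-week abstinence: "Weighted logistic regression will be used to estimate 24-week abstinence rates for each of the strategies". The parameters it lists are the initial randomization group plus site, age, gender and HSI. Weighting is there because re-randomized non-responders are split between two options. The output is stated as "Predicted probabilities and 95% confidence intervals will be estimated for each of the strategies", and the choice rule as "The strategy with the highest predicted probability will be identified as the optimal strategy".

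For CD4, viral load and VACS, section 9.4.2 says "weighted linear mixed models will be used to estimate mean outcomes at 12 and 24 weeks for each of the treatment strategies". That model has indicators for both randomizations and their interactions with time. Also, "A random effect will be included for repeated measures" and "Inverse probability weighting will be used to account for non-responders being re-randomized". No first-by-second-stage interaction is listed.

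Neither section gives numerical weights, says how a week-12 responder is coded for the second stage, names a variance estimator, or says how the weights enter the mixed model. Section 4.1 gives the first allocation ("participants will be randomized 1:1 to either NRT (nicotine replacement therapy) or NRT + CM") but no ratio for the second. It also says that responders continue unchanged, so they have no second-stage assignment.

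**The concern.** A week-12 responder is consistent with two of the four strategies, and a non-responder with one. Inverse-probability weighting repairs that imbalance only if each responder is counted under both second-stage options, the model can tell the four strategies apart, and the standard errors recognise that weights are not extra people and that a replicated responder is one person. The plan writes down the weighting and leaves out the rest.

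The trial's main question is which adaptive strategy is best. For abstinence, the strategy estimates in 9.4.8 are the plan's answer. Unwritten coding choices can change the intervals and, where they alter who counts toward which strategy, the estimates themselves. If such choices are made after the data are seen, analysts working from the same plan could name different best strategies.

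**Working it through.** **Inputs.** From 9.2: 187 randomized plus 19 × 5 = 282; after 20% loss, 282 × 0.8 = 225.6, taken as 226. Week-12 response is 7% (NRT) and 16% (NRT+CM), 11.5% overall. Week-24 abstinence in non-responders is 16% (switch) and 7% (intensify). These rates come from the original sample-size calculation. Assumed, because the documents do not say: re-randomization is 1:1, and 60% of responders are still abstinent at week 24 (100% was also run).

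**The plan's own figures.** It gives none for coverage or weights. As a check on the sample size, a two-sample t calculation with SD 7, two-sided alpha 0.025, 80% power and 112 per arm gives 2.90 cigarettes per day, as stated in 9.2.

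**1. Missing second-stage term.** A strategy's rate is r × 0.60 + (1 − r) × q, with r the response rate and q the second-stage rate:
- NRT then switch: 0.07 × 0.60 + 0.93 × 0.16 = 19.1%
- NRT then intensify: 0.07 × 0.60 + 0.93 × 0.07 = 10.7%
- NRT+CM then switch: 0.16 × 0.60 + 0.84 × 0.16 = 23.0%
- NRT+CM then intensify: 0.16 × 0.60 + 0.84 × 0.07 = 15.5%

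A model with only the initial group gives one prediction per arm at given covariates: two numbers, not four. With responders replicated they are 0.042 + 0.93 × 0.115 = 14.9% and 0.096 + 0.84 × 0.115 = 19.3%. With each responder entered once at weight 1 and each non-responder at weight 2, they are (0.042 + 2 × 0.93 × 0.115)/(0.07 + 2 × 0.93) = 13.3% and (0.096 + 2 × 0.84 × 0.115)/(0.16 + 2 × 0.84) = 15.7%.

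**2. Responder entry.** Suppose a second-stage term is added but responders are coded to one level only, here intensify. Both switch strategies then lose their responders and are estimated at 16% (from 23.0% and 19.1%), while NRT+CM then intensify stays at 15.5%. In simulation (N = 226, 60% sustained abstinence), the truly best strategy has the highest estimate in about 67% of trials with replication and about 34% with this coding. This is an illustration; the plan specifies no coding.

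**3. Interval coverage.** With 113 people per arm and r = 0.115, the people consistent with one strategy number 113 × (0.115 + 0.885/2) = 63. Weights 1 and 2 sum to 113; weights 2 and 4 sum to 226. The effective number, (Σw)²/Σw², is 113/(0.115 + 2 × 0.885) = 60. Model-based errors with raw weights are thus too small by about √(60/113) = 0.73 or √(60/226) = 0.52. The implied coverage, 2Φ(1.96 × ratio) − 1, is about 85% or 69%.

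That approximation treats responders and non-responders as equally variable. A simulation that does not (10,000 runs per setting, logit-scale intervals, responders replicated, no covariates or imputation) agrees closely with separate runs. The ranges across strategies and runs are:

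| Standard error | Coverage of nominal 95% interval |
|---|---|
| Model-based, raw weights 1 and 2 | about 86-90% |
| Model-based, raw weights 2 and 4 | about 70-76% |
| Model-based, weights normalized to record count | about 95-98% |
| Participant-clustered sandwich | about 95% |

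**4. Weights in the mixed model.** If the weight w divides only the residual variance, a person with m records counts as 1/[ICC + (1 − ICC)/(w·m)]. The model adjusts for baseline. Under an exchangeable correlation ρ, the remaining ICC is ρ/(1 + ρ): 0.33 at ρ = 0.5, and never above 0.5. The schedule in 1.3 shows HIV biomarkers at baseline and week 24 only (m = 1), whereas 9.4.2 models weeks 12 and 24 (m = 2). The responder share of a strategy mean is r/[r + (1 − r)/2 × ratio], with r = 0.115.

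| ICC | Records | Ratio reached (2 needed) | Responder share (11.5% correct) |
|---|---|---|---|
| 0.33 | 1 | 1.50 | 14.8% |
| 0.50 | 1 | 1.33 | 16.3% |
| 0.33 | 2 | 1.33 | 16.3% |
| 0.50 | 2 | 1.20 | 17.8% |

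With no weighting at all the share would be 20.6%. A robust standard error would not correct this, because the estimate itself is shifted.

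**The case against.** A reader might infer that the plan uses ordinary model-based errors and that its 95% intervals therefore under-cover badly. The documents do not support that. They name no variance estimator, a robust variance fits their wording, and normalized weights show no under-coverage. Nor do they state a 2:1 weight; it follows only if re-randomization is 1:1.

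It can also be said that promising four strategy rates implies a second-stage term, and that describing non-responders as under-represented relative to responders presupposes that responders are kept. Both are fair readings of intent, but the listed parameters still do not produce four rates, and keeping responders is not the same as entering them under both options. The mixed-model effect depends on the weight acting on the residual variance alone, which 9.4.2 does not say.

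The consequences are also bounded. Section 9.4.8 is exploratory and framed as estimation, and it selects on the point estimate, so interval coverage alone cannot change the winner. Section 9.1 sets no hypotheses for the HIV outcomes. Finally, leaving the mixed model gives up its likelihood-based handling of incomplete records. All of this stands; it limits the size of the point and adds a condition to the remedy.

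**Conclusion.** The point holds as a gap in the specified method. As written, the abstinence model cannot return four strategy rates, and neither analysis says how responders enter both strategies, what variance is used or, for the mixed model, how the weights act.

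Under-coverage is conditional: it arises if raw weights are combined with model-based errors, and disappears with normalized weights or a clustered sandwich. The mixed-model distortion is also conditional. If weights scale only the residual variance, re-randomization is 1:1 and the baseline-adjusted ICC is about 0.33-0.5, an intended 2:1 becomes about 1.3-1.5:1 with one post-baseline record or 1.2-1.3:1 with two. HIV-outcome strategy means then lean toward responders.

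The coverage figures rest on the response rates in 9.2 and an assumed 60% or 100% sustained abstinence, without covariates or imputation. The two primary tests in 9.4.1 do not use these models and are unaffected.

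**What to change.** In 9.4.2 (strategy means for HIV outcomes) and 9.4.8, replace the weighted mixed and logistic models with weighted-and-replicated estimating equations:

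- Include first-stage treatment, second-stage treatment, their interaction and the baseline covariates already listed, with time terms for the HIV outcomes.
- Enter each responder under both second-stage options and each non-responder once.
- State the second-stage allocation ratio. Set weights to the inverse of the actual randomization probabilities: 2 for responders and 4 for non-responders if both stages are 1:1.
- Use an independence working correlation, so that the weights act in full.
- Take 95% intervals from a participant-clustered sandwich or a participant-level bootstrap, pooled over imputations.
- Extend multiple imputation to the HIV outcomes, since the mixed model's likelihood handling of missing data is given up.

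The cost is SAP wording, standard code, and some extra analysis and imputation work. No visits or data are added. Intervals will be wider than raw-weight model-based ones, though not necessarily wider than those from normalized weights.

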2 INTRODUCTION

2.1 STUDY RATIONALE

The study aims to answer the main research question, what is the optimal, adaptive strategy to promote long-term (24 week) reduction in average daily cigarettes smoked among patients with HIV? The first aim is to identify the optimal adaptive approach to promote reduction in average cigarettes smoked per day among participants. The second aim is to identify the impact of various tobacco treatment regimens on promoting confirmed smoking abstinence and HIV-related biomarkers over time, including promoting improvements in: 1) CD4 count; 2) HIV viral load suppression; and 3) VACS Index scores within participants. The third aim is to conduct an implementation focused-evaluation of a clinical pharmacist-delivered intervention involving NRT, VAR, bupropion, and CM among all the stakeholders (clinicians, staff and leadership). Aim 3: To inform future implementation efforts of our clinical pharmacist-delivered intervention involving NRT, CM and varenicline and bupropion to promote smoking cessation among patients with HIV, we will conduct a comprehensive evaluation of factors that may impact delivery of this intervention in real-world settings. This evaluation will be based on recruitment experiences; surveys from clinicians, staff, clinical leadership, social workers, psychologists, and care coordinators; and costs associated with the intervention.

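### The exploratory strategy analysis names the highest of four abstinence estimates as optimal, without between-strategy differences or any allowance for having picked the maximum

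*Combined protocol and SAP*

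**What the plan says.** Section 9.4.8 (Exploratory Analyses) concerns abstinence at week 24. "There are four strategies to compare": NRT or NRT+CM first, each followed in non-responders by either the oral-medication switch or the CM intensification. The method is weighted logistic regression, with inverse probability weights because only non-responders are re-randomized.

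The output is one estimate and interval per strategy: "Predicted probabilities and 95% confidence intervals will be estimated for each of the strategies". The decision rule is "The strategy with the highest predicted probability will be identified as the optimal strategy", and the stated reason is "Choosing the optimal strategy is an estimation rather than hypothesis testing problem".

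The listed model terms are: "The analysis will include parameters for the initial randomization group as well as site, age, gender and HSI as baseline covariates". No second-stage term is listed, although the model for HIV outcomes in section 9.4.2 has indicators for both randomizations.

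Sections 9.4.1 and 9.4.2 compare NRT+CM with NRT, and switch with intensify among non-responders. For HIV outcomes, section 9.4.2 also estimates a mean per strategy. No section plans a difference between two of the four strategies.

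**The concern.** The largest of four noisy estimates is called optimal however close the others are. Separate intervals do not show whether two strategies differ, and here they are harder than usual to compare by eye, because the two strategies that start from the same initial arm share that arm's responders and are therefore correlated. The estimate of whichever strategy comes out on top is also biased upward by the act of selection, and the plan does not say so.

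At stake is how the result is read. A report that names one strategy as optimal, with its own CI and nothing else, invites more confidence in that choice and in its abstinence rate than the data can support at the reduced sample size.

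**Working it through.** **Inputs from the documents.** First-stage allocation is 1:1 (section 4.1). From section 9.2: projected N = 187 + 19 × 5 = 282; loss to follow-up 20%, so 282 × 0.8 ≈ 226 evaluable; week-12 abstinence 16% (NRT+CM) and 7% (NRT); week-24 abstinence in non-responders 16% (switch) and 7% (intensify).

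**Assumptions.** The second-stage ratio is not stated; independent 1:1 allocation is assumed. The share *s* of week-12 responders still abstinent at week 24 is not given; 60% to 100% is used. The four strategies are estimated separately, without covariates.

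**Plan's own figures.** The plan gives none for the selection rule, but its sample-size figures reproduce from the same inputs. A two-sample t-test with SD 7, two-sided alpha 0.025 and 80% power gives 2.89 cigarettes per day at 225.6 evaluable (plan 2.90) and 3.07 at 250 × 0.8 = 200 (plan 3.07). For the original design, 16% vs 7% at 85% power gives 538, as stated, and 538 / 0.85 = 632.9 (plan 632).

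**True strategy rates.** With response rate *r* and second-stage rate *q*, p = r·s + (1 − r)·q. At s = 60%:

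- NRT, then switch: 0.07 × 0.6 + 0.93 × 0.16 = 19.1%
- NRT, then intensify: 0.07 × 0.6 + 0.93 × 0.07 = 10.7%
- NRT+CM, then switch: 0.16 × 0.6 + 0.84 × 0.16 = 23.0%
- NRT+CM, then intensify: 0.16 × 0.6 + 0.84 × 0.07 = 15.5%

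**Standard errors.** Responders have weight 1 and non-responders weight 2. With n per initial arm,

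Var ≈ [ r{s(1−p)² + (1−s)p²} + 2(1−r){q(1−p)² + (1−q)p²} ] / n.

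For NRT+CM then switch, n = 113: (0.0603 + 0.2341) / 113 = 0.00261, so SE = 5.1 points. For NRT then switch the SE is 5.0. The gap between these two is 23.0 − 19.1 ≈ 4.0 points, and the SE of their difference is √(5.1² + 5.0²) ≈ 7.1 points.

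**Selection under the plan's effects** (at least 40,000 simulated trials per row):

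| Evaluable N | s | Best named | Mean overstatement of winner | Mean true-rate loss |
|---|---|---|---|---|
| 226 | 60% | 67% | 3.0 | 1.5 |
| 226 | 100% | 78% | 2.6 | 1.7 |
| 282 | 60% | 71% | 2.5 | 1.3 |
| 282 | 100% | 82% | 2.1 | 1.4 |

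The last two columns are in percentage points. Check on the loss in the first row: the second-best strategy is named in 27% of trials, the third in about 5% and the worst in 0.7%, so 0.27 × 4.0 + 0.05 × 7.6 + 0.007 × 12.3 ≈ 1.5. An exactly balanced second-stage split improves these figures slightly. With half the effects (226, s = 60%), the best is named in about 50% of trials.

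**Selection when all four are equal.** Take 11.5% at each stage, the mean of 16% and 7%. Each strategy is named in about 25% of trials. The expected maximum of four independent normal estimates lies 1.03 SE above the common mean. The SE runs from 4.1 (282, s = 60%) to 4.9 (226, s = 100%), so the overstatement is about 1.03 × 4.1 = 4.2 to 1.03 × 4.9 = 5.0 points. Simulation agrees. True rates are 17.1% (0.115 × 0.6 + 0.885 × 0.115) to 21.7%.

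**What a set of best would show.** Drop a strategy only if another beats it by more than 2.06 SE of their difference (one-sided Dunnett-type value for three comparisons). Under the plan's effects the set averages about three strategies. It holds all four in about 19-36% of trials and a single one in about 4-8%; the truly best stays in it in over 99%. Under equality, a single strategy remains in under 1%.

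**The case against.** The strongest reply is that picking the maximum is a deliberate and sound choice for a selection problem. Under exact equality any pick costs participants nothing. Under the plan's effects most wrong picks fall on the second-best strategy, and the average loss is 1.3-1.7 points. That stands, and it is why the rule should stay as a point choice.

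Second, the randomized contrasts on abstinence are already planned in section 9.4.2, and the difference between two strategies within an initial arm comes only from switch versus intensify. That is partly right. However, those contrasts are pooled over initial arms, and they give no difference between strategies that start in different arms.

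Third, 226 is a pessimistic size. Sections 9.3 and 9.4.2 keep nearly all randomized participants in the abstinence analysis and impute missing outcomes. This stands, although imputation restores only part of the information; hence the range from 226 to 282.

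Some stronger readings are tempting, but the documents do not support them:

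- **That this rule decides the trial's main aim.** Section 2.1 says "The first aim is to identify the optimal adaptive approach to promote reduction in average cigarettes smoked per day among participants", whereas the rule in 9.4.8 is on abstinence, a secondary outcome, and is labelled exploratory.
- **That an error rate is breached.** The analysis is described as estimation and no confirmatory claim rests on it.
- **That the winner is always overstated.** The bias is an average; even under equality about 9% of winners are not overstated.
- **That a single winner always emerges.** With only the terms listed, both strategies within an initial arm would get the same prediction, so the rule could not separate them. The figures here assume that this is not the intended model.

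**Conclusion.** The point holds as a minor one. Section 9.4.8 identifies an optimum from point estimates alone, and nothing elsewhere in the plan supplies strategy-level differences or a way to report that the strategies are not separated. At the projected size the SE of the difference between the two leading strategies (about 7 points at 226 evaluable, s = 60%) exceeds the gap that the plan's own rates imply (about 4 points). So roughly one trial in five to one in three would name a strategy that is not the best, and the reported rate would be a few points too high on average.

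The figures depend on the 16%/7% rates of the original calculation, the assumed 60-100% maintenance among responders, 1:1 re-randomization and separate estimation of the four strategies. Smaller true effects make correct selection less frequent and the overstatement larger.

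A reader might infer that a strategy should be called optimal only when it stands alone in the set of best. That is a debatable trade-off rather than a correction: under the plan's own effects it would name an optimum in only about 4-8% of trials.

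**What to change.** Keep the selection, change its label and add the comparisons. Suggested text for section 9.4.8:

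*The strategy with the highest predicted probability will be reported as the strategy with the highest estimated 24-week abstinence; this does not establish it as optimal. All six pairwise differences between the four strategies will be reported with simultaneous 95% confidence intervals, using a robust covariance that accounts for responders shared by strategies with the same initial treatment. The set of strategies not distinguishable from the best will be reported by multiple comparisons with the best. The estimate for the selected strategy will be accompanied by a statement that it is biased upward by selection.*

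In the same edit, state the second-stage term in the model, so that the four strategies are estimated separately.

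The cost is SAP wording and a few lines of code, with no new data, visits or participants. The downside is a less decisive report. Even if the plan's effects are real, the set will average about three strategies and will often hold all four, so the report will usually say that the data do not separate them.
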